5.3.2. Estimand

The primary estimand, the main clinical quantity of interest to be estimated in the study, is defined by the following components:

- Population: subjects of age 5 years or above with *RPGR-XLRP*
- Treatment: subretinal administration of AAV5-hRKp.RPGR at low and intermediate doses (pooled) for immediate treatment arm and 6-month deferred treatment for deferred treatment arm
- Variable: retinal sensitivity response defined by point-by-point data from 185-point static perimetry
- Intercurrent event: none
- Strategy for addressing intercurrent events: treatment policy strategy
- Population-level summary: Difference in the proportion of responders in retinal sensitivity between immediate treatment subjects and deferred treatment subjects and associated 95% confidence interval

5.3.3. Analysis Methods

Descriptive summaries by treatment group and time point (and study eye when appropriate) using descriptive statistics will be provided. Descriptive statistics such as mean, median, standard deviation, 95% CIs (when applicable), minimum, and maximum will be used to summarize continuous variables; counts and percentages will be used to summarize categorical variables. Change from baseline will be summarized in the same format and plotted across time by treatment group for primary and secondary endpoints.

The primary efficacy endpoint will be evaluated based on point-by-point data from 185-point static perimetry (excluding 3 loci near blind spot). Subjects will be considered a responder if they experience at least 7dB improvement from baseline in at 5 or more loci at Week 13 and Week 26. Subjects with missing visits in either Week 13 or Week 26 will not be counted as responder or non-responder and will not contribute to number of subjects in the denominator when calculating proportion of responders.

A Stratified Fisher's exact test (two-sided) will be used to evaluate the number of responders and non-responders in immediate (pooled low and intermediate doses) versus deferred treatment group

from the dose expansion phase of the study. The stratification factor is age at time of informed consent (<25 years, \geq 25 years). Point estimates with corresponding 95% confidence intervals will be provided for the difference in proportion of responders comparing between immediate vs. deferred treatment group. The proportion of responders and 95% confidence interval at week 52 in immediate treatment group (pooled low and intermediate doses) will also be estimated, where the responder is defined as a subject who experiences at least 7 dB improvement from baseline at 5 or more loci at Week 52 and one or more time point prior to Week 52.

The proportion of responders and 95% confidence interval through week 26 will be estimated and summarized by dose level (low and intermediate) and overall in a separate table for deferred subjects post treatment.

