5.5.2 Secondary Outcomes

The secondary outcomes are measures of the efficacy of the ATIMP; these will be performed on an individual participant basis and will be descriptive in nature.

- Slowing or halting of progressive deterioration in retinal structure or visual function that is greater
 than the baseline variation for that test and is sustained for at least 2 consecutive assessments.
 Slowing or halting of progression over time may be facilitated by comparing identical structural
 and functional assessments acquired prior to intervention/injection to better determine rate of
 change over time in this slowly progressive disease.
 - Historical images will be collected wherever possible with written informed consent from the participants
- Any improvements in visual function from baseline that are greater than the baseline variation and are sustained for at least two consecutive assessments.
- Any improvement in retinal function from pre-intervention that is greater than baseline variation and measurable by electrophysiology (pattern ERG, multifocal ERG or full-field ERG).
- Health- and Vision-Related Quality of life (HRQoL, VRQOL) will be assessed by the Impact of Visual Impairment (IVI) questionnaire, the Low Luminance Questionnaire (LLQ), the EQ5D HRQoL questionnaire (EQ-5D-5L or EQ-5D-Y), changes in disease severity and health status will be assessed by the Patient Global Impression of Severity (PGIS), the Patient Global Impression of Change (PGIC) and the Clinician Global Impression of Change (CGIC) measures.

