5.10.3.3 Statistical Methods – Secondary Outcome Analysis

The secondary outcomes are measures of the efficacy of the ATIMP; these will be performed on an individual participant basis and will be primarily descriptive in nature. Standard assessments will be used to measure visual function and established methods of analysis, appropriate for the assessment will be used to evaluate the data. For specialist assessments, data will be analysed by the expert team member(s) who developed the assessment. Final data will be reported descriptively.

Efficacy will be indicated by:

- 1) Slowing or halting of progressive deterioration in retinal structure or visual function that is greater than the baseline variation for that test and is sustained for at least 2 consecutive assessments.
- 2) Any improvement in visual function from baseline that is greater than the baseline variation for that test and is sustained for at least 2 consecutive assessments.
- 3) Any improvement in retinal function from baseline that is measurable by electroretinography (ERG)

Measures will be reported individually, in each dose, and aggregated across participants as the proportion who satisfy the above criteria.

Health- and vision-related quality of life (HRQoL, VRQoL) patient reported outcome and treatment experience interview data will be used to correlate a participant's feeling about their own wellbeing with clinical observations.

Any deviations from the original statistical plan will be approved by the IDMC and described in the final report, as appropriate.

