1. INTRODUCTION

This Statistical Analysis Plan (SAP) specifies definitions of analysis sets, key derived variables, and statistical methods for the analysis of safety and efficacy data for the Phase I/II RPGR study (MGT009). This SAP is based on the protocol of study MGT009, v12.0 and replaces the original SAP dated 24 May 2019, with the key change related to the analysis of efficacy parameters as further described in Section 5.1. Titles, mock-ups and programming instructions for all statistical outputs (tables, figures, and listings) are provided in a Data Presentation Specifications (DPS).

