5.1. Changes to the Protocol

This SAP will not define slowing or halting of progressive deterioration using baseline variation, as defined in Protocol v12.0. Instead, this SAP will assess the visual function endpoint readout in immediate treatment group compared with deferred treatment group.

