5.3. Primary Efficacy Endpoint

5.3.1. Definition

The primary efficacy endpoint is evaluated in subjects from the dose expansion phase based on point-by-point data from 185-point static perimetry assessed through Week 26 in the randomized immediate treatment subjects and compared with randomized deferred subjects in the 26-week deferred period (prior to treatment). Subjects will be considered a responder if they experience at least 7 dB improvement from baseline at 5 or more loci at Week 13 and Week 26; this determination will be based on the treated eye for subjects in the immediate treatment group and for the deferred participant treatment eye for subjects in the deferred group, who had static perimetry assessments at both Week 13 and Week 26. Subjects with missing visits in either Week 13 or Week 26 will not be counted as responder or non-responder and will not contribute to number of subjects in the denominator when calculating proportion of responders.

Treated eye refers to a treated eye in a participant who was assigned or randomized to immediate treatment in any period of the study. Randomized concurrent control eye refers to an untreated eye in a participant who was randomized to deferred treatment; these eyes will receive treatment after completion of the 6-month deferral period. For the purposes of the primary efficacy analyses, these eyes represent the randomized concurrent control group.

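### The Week 52 responder rule lets any earlier visit confirm the response, so it counts unsustained patterns and is not on the same footing as the Week 26 rule

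*SAP*

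**What the plan says.** SAP 5.3.1 defines the primary responder by "at least 7 dB improvement from baseline at 5 or more loci at Week 13 and Week 26", and SAP 5.3.3 repeats this. Participants missing either of those visits are left out of both numerator and denominator.

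SAP 5.3.3 then adds an estimate at Week 52, with a 95% confidence interval, for the pooled immediate-treatment group. Here the 7 dB gain must be present "at 5 or more loci at Week 52 and one or more time point prior to Week 52". The missing-visit sentence names Weeks 13 and 26 only; nothing equivalent is given for Week 52.

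The supplied protocol asks for persistence. Section 5.5.2 looks for improvements in visual function that "are sustained for at least two consecutive assessments", and section 5.10.3.3 asks for improvement "greater than the baseline variation for that test and is sustained for at least 2 consecutive assessments".

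SAP 5.1 lists one change from the protocol: "This SAP will not define slowing or halting of progressive deterioration using baseline variation, as defined in Protocol v12.0". It says nothing about consecutive confirmation of improvement. SAP section 1 states: "This SAP is based on the protocol of study MGT009, v12.0". The amendment log of the supplied protocol ends at v11.0.

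**The concern.** One endpoint has two persistence rules. At Week 26 the confirming visit is fixed and adjacent. At Week 52 it can be any earlier one, so a participant whose response was absent at Week 26 can still be counted as a Week 52 responder.

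This matters because of where the looser rule sits. The SAP drops the test-retest analysis (Amendment History and 5.2) on the ground that efficacy now rests on comparing immediate with deferred treatment. That comparison exists at Week 26. It does not exist at Week 52, because the control is the 6-month pre-treatment period of the deferred arm. With no control and no test-retest benchmark, repetition across visits is the main protection left against chance response, and the Week 52 rule relaxes it.

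A reader who sets the Week 52 proportion beside the Week 26 proportion to judge durability would be comparing two different definitions, and possibly two different denominators.

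**Working it through.** The documents give no expected responder rate, power or sample-size calculation for either rule, so there is no figure of the plan's own to reproduce. The two rules are compared directly.

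**Inputs**
- Week 26 rule: response at Weeks 13 and 26 (SAP 5.3.1, 5.3.3).
- Week 52 rule: response at Week 52 and at one or more earlier time points (SAP 5.3.3).
- Post-treatment static perimetry in the immediate arms: protocol Table 3, as extracted, shows Months 3, 6 and 12 and none at Month 9. The table is damaged and the SAP has a Week 39 window, so both two and three earlier visits are shown.
- Pooled immediate group: up to 32 (protocol 5.11.2).
- Per-visit probability p of meeting the 7 dB, 5-loci criterion: not given. Assumed equal at every visit and varied.

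**Patterns.** With two earlier visits, the Week 52 rule accepts everyone who responds at Weeks 26 and 52, plus those with the pattern yes–no–yes at Weeks 13, 26 and 52. That added pattern is the whole difference from a rule requiring Week 52 and the preceding visit. The preceding-visit rule is a subset of the SAP's rule, so the SAP's proportion can never be the lower of the two in the same participants; this needs no model.

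**Independent visits**
- Week 26 rule: p × p = p².
- Week 52 rule, two earlier visits: p[1 − (1 − p)²] = p² + p²(1 − p) = p²(2 − p). The ratio to the Week 26 rule is 2 − p.
- Week 52 rule, three earlier visits: p[1 − (1 − p)³].

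| p | Week 26 | Week 52, two earlier | Week 52, three earlier |
|---|---|---|---|
| 0.1 | 1.0% | 1.9% | 2.7% |
| 0.3 | 9.0% | 15.3% | 19.7% |
| 0.5 | 25.0% | 37.5% | 43.8% |

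At p = 0.3 and 32 participants, the expected counts are 32 × 0.09 = 2.9 and 32 × 0.153 = 4.9.

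**Correlated visits.** Every change score uses the same eye and the same baseline mean (SAP 2.6), so positive correlation is to be expected. A latent-normal simulation with equal correlation rho between visits (1,000,000 draws, two earlier visits) gives:
- rho = 0.7, p = 0.3: 19.1% at Week 26 and 23.7% at Week 52, ratio 1.24.
- rho = 0.9, p = 0.5: 42.8% and 46.3%, ratio 1.08.

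**If response differs at Week 52.** With independent visits and p = 0.3 at Weeks 13 and 26, the two proportions are equal when the Week 52 probability is 0.09 / 0.51 = 0.176. Below about 0.18 the Week 52 proportion would be the lower one.

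**Against the protocol's rule.** The protocol does not say which two consecutive assessments count. With three visits they can be Weeks 13 and 26 or Weeks 26 and 52, so under independence the probability is p² + p² − p³ = 2p² − p³ = p²(2 − p), the same as the SAP's Week 52 rule.

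**With the preceding visit required.** The Week 52 probability becomes p², equal to the Week 26 rule at equal p with independent visits: 9.0% at p = 0.3.

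**The case against.** A reader might infer that the SAP has set a lower bar than the protocol. The documents do not support that. The protocol accepts any two consecutive assessments and its structured summary places efficacy assessment between 3 and 12 months, so with three visits its rule has the same probability as the SAP's. The protocol also does not require response at Week 52, which the SAP does. The two differ in which patterns count: the protocol's excludes yes–no–yes, the SAP's accepts it. Whether v12.0 keeps the consecutive wording cannot be seen.

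A reader might also take the independence ratios (1.5 to 1.9 for p from 0.5 down to 0.1) as the size of the effect. They are an upper range, and the correlated cases are much smaller. Nor is the Week 52 proportion bound to exceed the Week 26 one: the rules are not nested, since someone can respond at Weeks 13 and 26 and fail at Week 52.

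The strongest defence is about importance. The Week 52 figure is a one-arm estimate with no hypothesis and no place in the testing sequence of SAP 5.5. Its definition is stated openly, and the SAP does not itself call it a measure of durability. The missing control follows from the deferred design, and no change of definition will supply one. SAP 1.2 reports delayed and missed visits from COVID-19, so a flexible confirming visit could be a sensible choice, though the SAP does not offer that reason. All of this stands and limits the point's weight. It does not make the two proportions comparable, nor make yes–no–yes a sustained response.

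**Conclusion.** The point holds as a minor one. The Week 52 definition counts a pattern that is not sustained over consecutive assessments, and SAP 5.1 does not declare this as a departure. The departure is shown against the supplied v11.0 only.

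At equal per-visit probability, the Week 52 rule is easier to meet than the Week 26 rule. With two earlier visits the excess ranges from a ratio of 2 − p under independence to 1.08 in the most strongly correlated case shown. The size rests on an assumed p, on p being the same at Week 52 as before, and on the number of earlier fields; a Month 9 field would widen the gap.

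The effect is confined to a descriptive, single-arm proportion outside the alpha sequence. A reader who inferred a threat to the primary comparison would be mistaken: it uses Weeks 13 and 26 only.

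**What to change.** In SAP 5.3.3, define the Week 52 responder as meeting the criterion at Week 52 and at the immediately preceding scheduled static perimetry visit. Name that visit from the schedule: Week 26 if there is no Month 9 field. State the same missing-visit and denominator rule as at Week 26. Report the any-earlier-visit proportion as supportive.

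Do not require the same loci to respond at both visits unless that is also applied at Week 26, where it is absent; adding it at Week 52 alone would break the comparability being sought. If the sponsor prefers its current rule, declare the departure in SAP 5.1 and show both proportions.

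The cost is one changed phrase and one added sentence, with no new data. The Week 52 rate may be lower, and a few participants who missed the preceding field will leave the denominator.

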5.4. Secondary Endpoints

5.4.1. Definition

Secondary efficacy endpoints will be analyzed as change from baseline through the week 26 assessment on treated eye in immediate treatment group and compared with deferred participant treatment eye in deferred treatment group at 26 weeks. Major secondary efficacy endpoints include the following:

- a) Central 30-degree hill of vision (V30) in static perimetry using visual field modeling and analysis (VFMA) (Richard Weleber, 2015)
- b) Average threshold in mesopic microperimetry
- c) Maze walk time in Vision Mobility Assessment (VMA) under 1 lux and 4 lux, where 4 lux will be tested first
- d) Low Luminance best corrected visual acuity (BCVA)
- e) Patient report outcome, Low Luminance Questionnaire (LLQ) for the assessment of functional vision in low light conditions
- f) Contrast sensitivity (Log CS) as measured by Pelli-Robson
- g) Area of Intact EZ under the fovea from Optical Coherence Tomography (OCT)

5.4.2. Analysis Methods

A linear mixed model will be used to model change from baseline V30 with treatment group, baseline V30, and visit month as fixed effect, subject as random effect and age group (<25 years vs. \geq 25 years) as strata in expansion phase. An unstructured correlation structure will be used to model within-subject correlations between different visits. Point estimates with corresponding 95% confidence intervals will be estimated for the difference in mean change from baseline between treated eye in immediate treatment group and deferred participant treatment eye in

deferred treatment group at week 26. Two-sided p-values will be reported. The mean change from baseline in V30 and 95% confidence interval at week 52 in immediate treatment group will also be estimated.

Other secondary endpoints will be analyzed through week 52 with the same methodology as described for V30. Possible transformations of the response (ie, logarithm) may also be considered as appropriate.

The mean change from baseline on V30 and other secondary endpoints and corresponding 95% confidence interval at week 26 will be estimated and summarized by dose level (low and intermediate) and overall in a separate table for deferred subjects post treatment.

For LLQ endpoint, the endpoint will be the change from baseline in average score across all item measures related to functional vision in low light conditions. The change from baseline in average score will be analyzed using the same methodology as described above for V30. The detailed analysis plan on patient reported outcome (PRO) will be documented in a supplementary PRO SAP separately.

[figure not shown]
For efficacy, if appropriate, a model-based imputation will be applied.

For a subject who either refuses or is unable to navigate the visual mobility assessment under a certain lux level, the missing data will be imputed using the predicted value from an imputation model based on Rubin's imputation strategy using SAS® PROC MCMC and MI, by leveraging data relevant to visual mobility assessment, such as age, lux level, test eye, treatment group and other baseline clinical covariates including static perimetry.

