1.3.2. Primary Efficacy Hypothesis

The objective of the dose expansion phase is to provide preliminary evidence of efficacy by comparing immediate treatment to a concurrent randomized control group. The randomized concurrent control eye refers to an untreated eye in a participant who was randomized to deferred treatment; these eyes are randomized and will receive treatment after completion of the 6-month deferral period. For the purposes of the primary efficacy analyses, these eyes represent the randomized concurrent control group. The primary comparisons of efficacy outcome assessments will be at Week 26 (immediate treatment vs. deferred treatment) in randomized expansion phase. Here immediate treatment group include subjects randomized to immediate low dose and immediate intermediate dose. Sensitivity analysis will also be conducted by pooling adult subjects from dose escalation and expansion phases together comparing immediate with deferred subjects.

The primary efficacy endpoint is responder/non-responder evaluated based on point-by-point data in full field from the 185-point (excluding 3 loci near blind spot) static perimetry assessed through Week 26 in the randomized immediate treatment subjects compared with randomized deferred subjects in the 26-week deferred period (prior to treatment). Subjects will be considered a responder if they experience at least 7 dB improvement from baseline at 5 or more loci at Week

26 and Week 13; this determination will be based on the treated eye for subjects in the immediate treatment group and for the deferred participant treatment eye in the deferred group, who had static perimetry assessments at both Week 13 and Week 26. The null hypothesis is that there is no difference in proportion of responders between randomized immediate treatment subjects and deferred treatment subjects. The alternative hypothesis is that the proportion of responders in the randomized immediate treatment subjects is greater than that in deferred subjects. The proportion of responders at Week 52 in subjects randomized for immediate treatment will also be estimated.

Table 1: loci near blind spot to be excluded from 185 loci grid for pointwise responder definition

| Eye | XPOS | YPOS |
|-------|-------|------|
| Left | -16 | -5.2 |
| Left | -13.9 | -1.2 |
| Left | -15 | 0 |
| Right | 16 | -5.2 |
| Right | 13.9 | -1.2 |
| Right | 15 | 0 |

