1.3.3. Secondary Efficacy Hypothesis

For the expansion phase, the null hypothesis for each secondary endpoint listed below is that there is no difference between the treated eye in subjects for the immediate treatment at Week 26 and the deferred participant treatment eye in the deferred group during 26-Week deferred period prior to treatment. The alternative hypothesis for each secondary endpoint listed below is that the improvement in the ATIMP treated eye in immediate treatment subjects is greater than that on the deferred participant treatment eye during deferred period prior to treatment.

- a) Central 30-degree hill of vision (V30) in static perimetry using visual field modeling and analysis (VFMA) (Richard Weleber, 2015)
- b) Average threshold in mesopic microperimetry
- c) Maze walk time in Vision Mobility Assessment (VMA) under lux 1 and lux 4, separately
- d) Low Luminance visual acuity (LLVA)
- e) Patient report outcome, Low luminance questionnaire (LLQ) for the assessment of functional vision in low light conditions
- f) Contrast sensitivity (Log CS) as measured by Pelli-Robson
- g) Area of Intact EZ under the fovea from Optical Coherence Tomography (OCT)

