2. GENERAL ANALYSIS DEFINITIONS

2.1. Visit Windows

The following rules are applied to assign actual visits to analysis visit windows. If a subject has two or more actual visits in 1 visit window, the visit closest to the target day will be used as the protocol visit for that visit window. The additional visit(s) will not be used in the summaries or analyses, but they can be used for determination of clinically important outcomes. If two actual visits are equidistant from the target day within a visit window, the later visit is used. All assignments will be made in chronological order. Once a visit date is assigned to a visit window, it will no longer be used for a later time point. If a visit falls outside of the visit window, then this visit will be assigned to the closest window according to the distance to the target day and visit description, if there is no visit assigned to the visit window.

Table 1: Visit Windows

| Dose Escalation Phase, Pediatric Dose Confirmation Phase, and Immediate Treatment Arms of Expansion Phase | | |
|--|----------------------|-------------------|
| Visit Window Label | Time Interval | Target Day |
| Baseline | -6 Months - Day -1 | < Day 1 |
| Day 1 (ATIMP admin.) | Day 1 | Day 1 |
| Day 2 | Day 2 | Day 2 |
| Day 4 | Day 3 – Day 5 | Day 4 |
| Week 1 | Day 6 – Day 10 | Day 8 |
| Week 2 | Day 11 – Day 21 | Day 15 |
| Week 4 | Day 22 – Day 36 | Day 29 |
| Week 6 | Day 37 – Day 56 | Day 43 |

| Week 9 | Day 57 – Day 72 | Day 64 | |
|---|----------------------|---------------------|------------|
| Week 13 | Day 73 – Day 160 | Day 92 | |
| Week 26 | Day 161 – Day 259 | Day 183 | |
| Week 39 | Day 260 – Day 350 | Day 274 | |
| Week 52 | Day 351 – Day 393 | Day 365 | |
| Deferred Treatment Arms of Expansion Phase | | | |
| Period | Visit Window Label | Time Interval | Target Day |
| Deferred Period (prior to treatment) | Baseline | -6 Months - Day 1 | ≤ Day 1 |
| | Week 13 | Day 73 – Day 168 | Day 92 |
| | Week 26 | Day 169 – Day 365 † | Day 183 |
| Post treatment period | Day 1 (ATIMP admin.) | Day 1 | Day 1¶ |
| | Day 2 | Day 2 | Day 2¶ |
| | Day 4 | Day 3 – Day 5 | Day 4¶ |
| | Week 1 | Day 6 – Day 10 | Day 8¶ |
| | Week 2 | Day 11 – Day 21 | Day 15¶ |
| | Week 4 | Day 22 – Day 36 | Day 29¶ |
| | Week 6 | Day 37 – Day 56 | Day 43¶ |
| | Week 9 | Day 57 – Day 72 | Day 64¶ |
| | Week 13 | Day 73 – Day 160 | Day 92¶ |
| | Week 26 | Day 161 – Day 365 † | Day 183¶ |

¶: after ATIMP administration day for deferred subjects

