5.5. Multiplicity Adjustment

A branched fixed sequence method will be used to control the family-wise type I error rate at 0.05 for testing the primary and key secondary endpoints comparing immediate treatment subjects (pooled low and intermediate doses) with deferred treatment subjects in the expansion phase as illustrated in Figure 3. Alpha of 0.05 will be allocated to the primary endpoint, static perimetry responder by pointwise analysis. If statistically significant, the alpha of 0.05 will be passed down to the first secondary endpoint, V30. If V30 is statistically significant, the alpha of 0.05 will be passed down to the visual mobility assessment. If the visual mobility assessment is statistically significant, MAIA microperimetry and patient report outcome (Impact of Vision Impairment – 'Reading and Accessing Information' domain) will be tested under alpha=0.04 and 0.01, respectively. If one or both endpoints are statistically significant, the remaining alpha will be passed down to test low luminance BCVA, contrast sensitivity and EZ area, conditional on the statistical significance of the prior test. If any of the endpoint(s) are not statistically significant, the allocated alpha for testing cannot be passed and testing will stop after all alpha has been spent.

Figure 3: Illustration of alpha distribution

Key: V30=central 30-degree hill of vision. MAIA =microperimetry

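### The V30 mixed model in SAP 5.4.2 has no treatment-by-visit term, so its Week 26 difference blends the Week 13 and Week 26 effects

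*SAP*

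**What the plan says.** SAP 5.4.2 describes the V30 analysis as a linear mixed model that will "model change from baseline V30 with treatment group, baseline V30, and visit month as fixed effect, subject as random effect". Age group (<25, ≥25 years) enters as strata, and the within-subject correlation is unstructured. No interaction is listed there or elsewhere in the SAP or protocol.

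The quantity wanted is tied to Week 26:

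- SAP 5.4.2 asks for the difference in mean change between the treated eye and the "deferred treatment group at week 26. Two-sided p-values will be reported".
- SAP 5.4.1 has the treated eye "compared with deferred participant treatment eye in deferred treatment group at 26 weeks".
- The null hypothesis in SAP 1.3.3 is that "there is no difference between the treated eye in subjects for the immediate treatment at Week 26" and the deferred eye.

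Both arms supply two post-baseline perimetry visits before the deferred arm is treated. SAP 1.3.2 bases the primary endpoint on participants "who had static perimetry assessments at both Week 13 and Week 26", and the deferred-period windows in SAP 2.1 include "Week 13 | Day 73 – Day 168 | Day 92" as well as Week 26. Later visits exist in the immediate arm only; for these SAP 5.4.2 adds that "The mean change from baseline in V30 and 95% confidence interval at week 52 in immediate treatment group will also be estimated".

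V30 comes straight after the primary endpoint in SAP 5.5: "If statistically significant, the alpha of 0.05 will be passed down to the first secondary endpoint, V30". SAP 5.4.2 applies the same method to the other secondary endpoints.

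**The concern.** With categorical visit and no interaction, the model forces the two arms' mean profiles to be parallel. It returns the same between-arm difference at Week 13 and at Week 26. That number is a generalised-least-squares weighting of the two visit differences, with weights set by the visit SDs and their correlation. The unstructured covariance does not repair this. It models the dependence between visits, not the means, and it is what determines the weights.

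A treatment effect may well change between three and six months. If it builds up, the reported Week 26 effect is too small and, when the build-up is steep, power is lost. If it fades, the test can reject when nothing remains at Week 26. In both cases the 95% interval under-covers the Week 26 effect. Because V30 is first after the primary endpoint, failure there stops all later testing. The primary responder test and the safety objective are not affected.

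**Working it through.** The plan gives no V30 power, SD, correlation or effect size (protocol 5.7 states that there is no formal sample size calculation), so there is no figure to reproduce. The check derives what the listed model estimates and sizes the consequence under stated assumptions.

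**Inputs from the documents.** Pooled immediate arm up to 32, deferred arm up to 16 (protocol 5.9.1); two-sided 0.05 (SAP 5); shared visits Week 13 and Week 26.

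**Assumptions.** Complete data, visit categorical, correlation r = 0.5 to 0.7, effects in Week 13 SD units, 45 degrees of freedom. Let s be the Week 26 SD divided by the Week 13 SD, tried at 1.0, 1.2 and 0.8.

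**Formulas.**

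- Weights: w26 = (1 − r·s)/(1 + s² − 2·r·s), and w13 = 1 − w26.
- Standard error of the Week 26 contrast: SE26 = s·√(1/32 + 1/16) = 0.306·s.
- Standard error of the common effect: SEc = 0.306·√[s²(1 − r²)/(1 + s² − 2·r·s)].
- Estimate under effects d13 and d26: w13·d13 + w26·d26. Power is from the noncentral t.
- Break-even Week 13/Week 26 effect ratio, below which the listed model has less power: k = (SEc/SE26 − w26)/w13.

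**Worked case, s = 1, r = 0.5.** w26 = 0.5/1 = 0.50. SEc = 0.306·√0.75 = 0.265. With effects 0.5 then 1.0, the estimate is 0.25 + 0.50 = 0.75 and the noncentrality is 0.75/0.265 = 2.83, giving 79% power. The Week 26 contrast has 1.0/0.306 = 3.27, giving 89%. Break-even is (0.866 − 0.50)/0.50 = 0.73.

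**Results. Each range covers r = 0.5 to 0.7; power and rejection are listed model vs Week 26 contrast.**

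| | s = 1.0 | s = 1.2 | s = 0.8 |
|---|---|---|---|
| Week 13 weight | 0.50 | 0.68-0.79 | 0.29-0.15 |
| SEc/SE26 | 0.87-0.92 | 0.78-0.82 | 0.95-0.99 |
| Steep build (0.5, 1.0): estimate | 0.75 | 0.61-0.66 | 0.86-0.92 |
| Steep build: power | 74-79% vs 89% | 50-62% vs 76% | 95-96% vs 98% |
| Steep build: coverage | 83-84% | 73-77% | 89-92% |
| Mild build (0.8, 1.0): power | 88-91% vs 89% | 78-84% vs 76% | 97-98% vs 98% |
| Mild build: coverage | 93-94% | 91-93% | 94-95% |
| Fade (0.8, 0): rejection | 28-31% vs 5% | 46-54% vs 5% | 8-16% vs 5% |
| Break-even k | 0.73-0.84 | 0.67-0.77 | 0.81-0.94 |

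Coverage is of the true Week 26 effect by the listed model's interval, simulated with the covariance estimated (20,000 trials per setting, unadjusted standard errors). A small-sample correction raises steep-build coverage to 85-87%, 77-80% and 91-94%. At s = 1 it also lowers fade rejection to 23-28% and steep-build power to 68-76%.

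**Constant effect of 0.8, s = 1.** The listed model is unbiased, with power 79-84% against 73%.

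**No effect at either visit.** Simulated rejection is 5.1-5.7% unadjusted and 4.8-5.1% corrected.

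**Later immediate-arm visits.** With categorical visit, adding Weeks 39 and 52 leaves the common estimate (0.750) and its standard error (0.265 at s = 1, r = 0.5) unchanged. If visit month were linear instead, Week 52 would also take weight: with equal SDs, 0.56, 0.39 and 0.05 on Weeks 13, 26 and 52. With the interaction, the Week 26 contrast puts all its weight on Week 26 and remains estimable although the deferred arm has no Week 39 or 52 data.

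**The case against.** The strongest reply is that the paragraph is a prose summary, not a model statement. It pairs a subject random effect with an unstructured covariance, which are not separately identifiable, and it does not say how age enters. It asks for visit-specific results at Weeks 26 and 52, so by-visit estimation was probably intended, and the Data Presentation Specifications, not among the documents reviewed, may supply the term. This stands as a comment on intent. But the text lists its fixed effects, and two programmers following it could obtain different p-values for an alpha-controlled endpoint.

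A second reply is that some phrases, such as analysing change through Week 26 (SAP 5.4.1), leave room for a deliberate average over the period. The request for a difference at Week 26 in SAP 5.4.2 favours the other reading. If an average is wanted, it should be named.

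Third, the size is wholly assumed and cuts both ways. That is correct. Power is similar or better under a mild build-up and better under a constant effect. The weights also depend on the covariance: at s = 0.8 and r = 0.8 the Week 13 weight is zero and the listed model returns exactly the Week 26 difference, while at r = 0.9 the weight is negative (−0.4).

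Fourth, the fade figures ignore the gate. V30 is tested only if the primary endpoint succeeds, and that requires a response at both visits, so a fade to zero would rarely reach the V30 test. The gated risk was not quantified.

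Finally, the trial is Phase I/II with a safety primary objective, and by-visit summaries and plots are planned (SAP 5.3.3). These would reveal a divergence but would not change what is tested.

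**Conclusion.** The concern holds. As written, the model cannot estimate the Week 26 difference that the plan names unless the effect is constant between Week 13 and Week 26, apart from special covariance patterns. The SAP neither states nor justifies a constant effect.

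The omission is certain from the text; the size is conditional on the assumed SDs, correlations and effects. The estimate and interval are wrong for Week 26 whenever the effect changes between visits. Power is lost only when the Week 13 effect is below roughly 67-94% of the Week 26 effect, depending on the covariance. False rejection under the complete null is not a problem, and for V30 the primary gate limits it under a fade.

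High confidence applies to V30 only. The same method is set for the other secondary endpoints, and mobility, contrast sensitivity, EZ area and microperimetry appear to be affected. However, the protocol supplied has an amendment log ending at v11.0, the SAP cites v12.0, and the microperimetry row in the extracted schedule is incomplete. This should be fixed, but it does not undermine the primary analysis.

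**What to change.** In SAP 5.4.2, state that visit is categorical, add treatment-by-visit to the fixed effects, keep baseline V30 and the age stratum, and use an unstructured within-subject covariance. Say whether the separate subject random effect is dropped, since the unstructured matrix makes it redundant. Define the tested quantity as the immediate-minus-deferred contrast at Week 26.

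Either restrict the between-arm model to Weeks 13 and 26 or define means by arm and visit, and take the Week 52 immediate-arm mean from its own cell or a separate analysis. The restriction is for clarity, since later visits do not distort the contrast when visit is categorical. A small-sample method such as Kenward-Roger is a sensible addition at this size. The effect averaged over Weeks 13 and 26 can be reported as supportive. Apply the same wording to each other secondary endpoint confirmed under protocol v12.0 to have both visits in both arms.

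The change is SAP wording and one model statement. Its price is precision if the effect is truly constant: under the assumptions above, the standard error is 8-15% larger with equal SDs, 1-6% larger at SD ratio 0.8 and 22-29% larger at ratio 1.2. It does not remove the separate difference in Week 26 windows in SAP 2.1 (Days 169-365 deferred, Days 161-259 immediate).
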